#### 5.2.2.7 Management of CMP-001 toxicity

##### CMP-001 Associated Adverse Events

If subjects develop inflammation at the injection site this may be managed using cold compresses and/or acetaminophen or non-steroidal anti-inflammatory agents. If flu-like symptoms (i.e., fever, myalgia, and headache) arise, these may be managed using acetaminophen or non-steroidal anti-inflammatory agents.

[figure not shown]
It is expected that symptoms associated with a large release in cytokines at the time of injection could present 1-4 hours after the injection. These symptoms could include: fever, nausea/vomiting, chills/rigors, and hypotension. Subjects must remain in observation until all of these symptoms have resolved to  $\leq$  Grade 1. Refer to **Table 4.1.4-1** for current CMP-001 safety profile in the ongoing CMP-001-001 clinical study.

Subjects who experience a DLT will have dosing of CMP-001 withheld until the toxicity has returned to  $\leq$  Grade 1. If the Investigator determines that continued treatment with CMP-001 is in the subject's best interest, treatment may resume at a reduced dose of CMP-001. Only one dose reduction is allowed. Subjects who still experience DLTs at Dose Level-1 must come off study.

#### CMP-001 Associated Cytokine Release-like Syndrome

As noted in **Section 4.2.2**, CMP-001 has been associated with symptoms associated with cytokine release. Most notable severe cases of hypotension have been noted, most often in subjects with a prior medical history of adrenal insufficiency secondary to ipilimumab. The backbone of the recommended treatment algorithm is the use of stress dose steroids and the IL6 antagonist tocilizumab (Maude et al. 2014; Lee et al. 2014; Tanaka et al. 2016; Brudno and Kochenderfer 2018).

The recommended algorithm for the treatment of symptoms associated with cytokine release below has been adapted for the treatment of cytokine release syndrome resulting from other immunotherapies such as CAR-T cell therapy (Lee et al. 2014) and is depicted in **Figure 4**. However, its effectiveness in treating symptoms associated with cytokine release resulting from CMP-001 has not been previously studied. The first line of treatment for hypotension unresponsive to supportive care such as fluids, is stress dose steroids as outlined below. Additional treatment measures include the use of drugs targeting specific cytokines believed to be involved in the development of cytokine release syndrome-induced hypotension. It is recommended that the treatment algorithm be implemented in subjects who present with acute hypotension following injection of CMP-001.

**Figure 4: Management of CMP-001 Associated Cytokine Release-like Syndrome**

#### **5.2.2.8    Changing the selected tumor**

Therapy of a selected lesion generally should continue per protocol unless the tumor is EITHER dramatically responding clinically OR dramatically progressing clinically. Inflammation of the injected tumor is expected following the 2nd and subsequent injections, but should not be mistaken for anti-tumor response or clinical progression.

If during therapy the injected tumor is clearly involuting and shrinking, and if a different eligible accessible tumor is progressing, then the Investigator should change the selection to the progressing tumor, injecting the full dose of CMP-001 into that tumor(s), and continuing to inject the new tumor(s) until EOT (or that tumor shows involution, in which case a third progressing tumor may be selected). If during therapy the injected tumor is clearly involuting and shrinking, and no other lesions are present, CMP-001 may be omitted or injected subcutaneously at the discretion of the treating investigator in consultation with the Principle Investigator.

If during therapy the injected tumor progresses, the treating investigator in consultation with the Principle Investigator may elect to continue therapy or transition to surgery directly. Every effort should be made to complete 7 weeks of perioperative therapy. The decision to proceed with surgery should be made (in consultation with the initial evaluating surgical oncologist) only if there is a danger of the subject being rendered inoperable.

### **5.3    Treatment Allocation**

During the Prime Phase, patients will receive nivolumab 240mg every 2 weeks in combination with CMP-001 5mg (week 1), and CMP-001 10mg intra-tumorally (weeks 2-7). Subsequently patients will undergo surgical resection.

During the Boost Phase, patients will receive nivolumab either 240mg every 2 weeks (or 480mg every 4 weeks) at Investigator's discretion along with CMP-001 5mg every 4 weeks.

### **5.4    Stratification**

None.

### **5.5    Concomitant Medications**

Medications or vaccinations specifically prohibited in the exclusion criteria are not allowed during the ongoing trial. If there is a clinical indication for one of these or other medications or vaccinations specifically prohibited during the trial, discontinuation from trial therapy or vaccination may be required. The investigator should discuss any questions regarding this with the principal investigator. The final decision on any supportive therapy or vaccination rests with the investigator and/or the subject's primary physician. However, the decision to continue the subject on trial therapy or vaccination schedule requires the mutual agreement of the treating physician investigator, the principal investigator, and the subject.

#### **5.5.1    Acceptable Concomitant Medications**

All treatments that the investigator considers necessary for a subject's welfare may be administered at the discretion of the investigator in keeping with the community standards of medical care. All concomitant medication will be recorded on the case report form (CRF) including all prescription, over-the-counter (OTC), herbal supplements, and IV medications and fluids. If changes occur during

the trial period, documentation of drug dosage, frequency, route, and date may also be included on the CRF.

All concomitant medications received within 28 days before the first dose of trial treatment and 30 days after the last dose of trial treatment should be recorded. Concomitant medications administered after 30 days after the last dose of trial treatment should be recorded for SAEs and ECIs as defined in **Section 7.2**.

### **5.5.2 Prohibited Concomitant Medications**

Subjects are prohibited from receiving the following therapies during the Screening and Treatment Phase (including retreatment for post-complete response relapse) of this trial:

- Anti-cancer systemic chemotherapy or biological therapy
- Immunotherapy not specified in this protocol
- Chemotherapy not specified in this protocol
- Investigational agents other than CMP-001
- Radiation therapy

Live vaccines within 30 days prior to the first dose of trial treatment and while participating in the trial. Examples of live vaccines include, but are not limited to, the following: measles, mumps, rubella, chicken pox, yellow fever, rabies, BCG, and typhoid (oral) vaccine. Seasonal influenza vaccines for injection are generally killed virus vaccines and are allowed; however intranasal influenza vaccines (e.g. Flu-Mist®) are live attenuated vaccines, and are not allowed.

Glucocorticoids for any purpose other than to modulate symptoms from an event of clinical interest of suspected immunologic etiology. The use of physiologic doses of corticosteroids may be approved after consultation with the Principle Investigator.

Subjects who, in the assessment by the investigator, require the use of any of the aforementioned treatments for clinical management should be removed from the trial. Subjects may receive other medications that the investigator deems to be medically necessary.

The Exclusion Criteria describes other medications which are prohibited in this trial.

There are no prohibited therapies during the Post-Treatment Follow-up Phase.

Agents known to have TLR9 antagonist activity are prohibited throughout the study. The known antagonists are chloroquine, hydroxychloroquine, and quinacrine.

Medications intended solely for supportive care (i.e., antiemetics, analgesics, megestrol acetate for anorexia) are allowed.

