### **5.2.2.1 Recommended prophylaxis**

To reduce the severity of symptoms associated with CMP-001 induced cytokines, prophylaxis is strongly recommended. Prophylactic regimens already in place at institutions should be followed, if not, below is a suggested regimen that has been effective for the treatment of CMP-001 induced adverse events:

- Fluids (e.g. 1000 cc IV normal saline)
- NSAIDS (e.g. 1000 mg acetaminophen and 50 mg Indomethacin)
- Anti-emetics (e.g. 8 mg Zofran PO)
- Hydrocortisone prophylaxis (50-100mg hydrocortisone – only for patients with prior G2-3 CRS-like reaction)

If an Investigator incorporates prophylaxis, administration should occur 30 minutes prior to intra-tumoral injection of CMP-001. It is also highly recommended to continue to run additional fluids immediately following the CMP-001 injection, rather than waiting to initiate fluids when hypotension is detected. There is no waiting period between the end of prophylaxis and the start of CMP-001 intra-tumoral injection. All treatments given prophylactically pre-and post CMP-001 dosing should be recorded on the Prior and Concomitant Medications eCRF separately for each visit where it is given.

**IMPORTANT:** Subjects with a history of adrenal insufficiency are at increased risk for moderate to severe adverse events such as hypotension which may occur with 1-4 hours after injection. It is strongly recommended that these subjects receive stress dose steroids (eg. 50-100 mg hydrocortisone PO q 8 hours) prior to, or immediately after injection of CMP-001.

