## 5.7 Subject Withdrawal/Discontinuation Criteria

Subjects are free to withdraw from the study at any time and without penalty or loss of future medical care, or any other benefits to which they are otherwise entitled. Subjects may discontinue study medication for any of the following conditions:

- Dose-limiting or other unacceptable toxicity considered to be related to either study medication;
  - Patients who develop unacceptable toxicity deemed related to CMP-001 but not Nivolumab may continue Nivolumab after CMP-001 discontinuation for duration as defined in **Section 5.2.2.4**.
  - Patients who develop unacceptable toxicity deemed related to Nivolumab but not CMP-001 must discontinue **both CMP-001 and Nivolumab**.
- PD by RECIST (Version 1.1) if accompanied by medically significant clinical deterioration, in the judgment of the Investigator. (Continuation of treatment through suspected pseudo-progression is permitted.);
- If, in the opinion of the Investigator, it is medically necessary;
- Subject withdraws consent for the study (note that subjects who withdraw consent for additional study treatment and procedures will continue to be followed for long-term survival unless they explicitly withdraw consent for any follow-up);
- Subject develops an intercurrent illness or adverse event that precludes further participation, or requires a prohibited concomitant treatment;
- Subject becomes pregnant or begins breastfeeding;

- Subject is lost to follow-up.

Subjects discontinuing study medication earlier than planned or withdrawing from the study should undergo the subsequent End of Treatment (EOT) clinical and laboratory assessments as soon as possible after study medication is stopped and the requisite safety follow-up period of 30 days should also be followed. The reason for withdrawal will be recorded in the electronic case report form (eCRF) and the subject's source medical record. All subjects will continue to be followed every three months after the last CMP-001 treatment for long-term survival follow-up until death, loss to follow-up, or withdrawal of consent for follow-up.

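### Section 5.5.2 bans glucocorticoids without exempting the stress-dose cover that section 5.2.2.1 strongly recommends for subjects with a history of adrenal insufficiency

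*Combined protocol and SAP*

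**What the plan says.** Section 5.5.2 (Prohibited Concomitant Medications) applies during Screening and the Treatment Phase. Among the prohibited therapies it names "Glucocorticoids for any purpose other than to modulate symptoms from an event of clinical interest of suspected immunologic etiology". It then adds one conditional allowance: "The use of physiologic doses of corticosteroids may be approved after consultation with the Principle Investigator". The consequence follows: subjects who, in the investigator's assessment, "require the use of any of the aforementioned treatments for clinical management should be removed from the trial".

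Section 5.7 (Subject Withdrawal/Discontinuation Criteria) includes among the conditions for which study medication may be discontinued: "Subject develops an intercurrent illness or adverse event that precludes further participation, or requires a prohibited concomitant treatment".

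Section 5.2.2.1 (Recommended prophylaxis) contains two uses of steroid:

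- For subjects with a history of adrenal insufficiency, who are flagged as being at higher risk of events such as hypotension: "It is strongly recommended that these subjects receive stress dose steroids". The example is "50-100 mg hydrocortisone PO q 8 hours", given before or straight after the CMP-001 injection.
- Within the suggested prophylactic regimen, hydrocortisone 50-100 mg, "only for patients with prior G2-3 CRS-like reaction". The aim stated for the regimen is "To reduce the severity of symptoms associated with CMP-001 induced cytokines".

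Neither 5.5.2 nor 5.7 refers to 5.2.2.1.

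**The concern.** One section strongly recommends a drug for a defined risk group. Another prohibits that drug for almost every purpose and attaches removal from the trial to needing it. A site following 5.5.2 and 5.7 to the letter would either take the subject off treatment or withhold the cover. A site following 5.2.2.1 would give the cover and have a prohibited medication on record.

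What is at stake is patient safety and consistent conduct. The risk group is one the protocol itself identifies: section 5.2.2.7 says severe hypotension on CMP-001 was seen most often in subjects whose adrenal insufficiency followed ipilimumab, and section 5.1.3 lets patients with prior ipilimumab enrol.

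**Working it through.** The plan states no figure on this point, so the check compares the texts. Arithmetic comes in only to show how often the question recurs.

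**Does either exception in 5.5.2 cover the adrenal-insufficiency cover in 5.2.2.1?**

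1. *Symptom modulation of an immunologic event of clinical interest.* Section 7.1.3.1 uses that term for adverse events of potentially immunologic origin. Section 7.2.5.2 lists only overdose and injection-site cutaneous events. The choice between them does not matter here. The cover is given before or immediately after injection, while 5.2.2.1 places the hypotension 1-4 hours later. There is normally no event yet whose symptoms could be modulated.
2. *Physiologic doses.* Section 5.2.2.1 calls the treatment a stress dose, not a physiologic one. Even if a clinician regarded it as physiologic, 5.5.2 would require approval after consultation, a step that 5.2.2.1 does not mention.

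The cover therefore clearly fits neither exception.

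**What about the other steroid uses?**

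- Hydrocortisone after an earlier G2-3 CRS-like reaction is less clear-cut. It belongs to a regimen that is only suggested, and its aim is to lessen symptoms, so it arguably falls under the first exception.
- Treating a CRS-like reaction under 5.2.2.7 is read here as inside the first exception, taking the broader sense of 7.1.3.1.

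**Can such subjects be in the trial?**

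- Exclusion 13 in 5.1.3 allows prior ipilimumab.
- Exclusion 7 lets subjects on 10 mg of steroid daily or less enrol without stopping.
- Exclusion 3 bars systemic steroid therapy within 7 days of the first dose, which may narrow the group. It does not bar a history of adrenal insufficiency as such.

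**How often does the question recur for one subject?**

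- CMP-001 doses: 7 in the Prime Phase and 12 in the Boost Phase (sections 6.1 and 7.1.1). Maximum if all are given: 7 + 12 = 19. This counts subcutaneous and intra-tumoral doses, because the adrenal-insufficiency paragraph does not limit the route.
- Example dose: 50-100 mg per administration. If dosing every 8 hours ran for 24 hours (an assumption, since 5.2.2.1 gives no duration): 3 × 50 = 150 mg to 3 × 100 = 300 mg.
- For the arguable post-CRS use: section 4.1.4 says the acute reactions typically appear after the third dose. If that timing carries over, 7 − 3 = 4 Prime Phase injections remain.

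**The case against.** The strongest reply is that the protocol's intent is plain and the conflict is only a missing cross-reference. Several points support this:

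- Section 5.2.2.1 asks that prophylactic treatments around each CMP-001 dose be logged as concomitant medication visit by visit. That presupposes subjects who receive them and stay on treatment.
- Section 5.2.2.7 makes stress-dose steroids part of the backbone of its treatment algorithm. A trial-specific safety instruction would naturally be taken to override a general list.
- The removal rule in 5.5.2 depends on the investigator's assessment. Section 5.7 is permissive, and its bullet opens with a newly arising illness or event, which a prior history is not.
- Section 5.5 says discontinuation may be required, not that it must be. It leaves supportive therapy to the investigator or primary physician, and it gives a route to continue by agreement of the treating physician, the principal investigator and the subject.
- Section 5.5.1 allows treatment needed for the subject's welfare, and 5.5.2 allows supportive-care medication.
- The hypotension remark comes from earlier CMP-001 experience. This trial's PD-1 naive population may differ.

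Most of this stands as evidence of intent and makes withholding the cover less likely. It does not remove the conflict. No provision exempts the cover or says that 5.2.2.1 takes precedence, and 5.5.2 names glucocorticoids specifically while 5.5.1 speaks generally. The supportive-care examples in 5.5.2 do not include steroids. The route in 5.5 protects giving the drug, but it makes continuing trial therapy a three-party decision that 5.2.2.1 does not foresee.

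**Conclusion.** The concern holds. Two stated rules conflict for subjects with a history of adrenal insufficiency, and the text does not settle which governs. For hydrocortisone after a CRS-like reaction the conflict is only arguable. For treatment of such a reaction there is none on the reading adopted here.

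The number of patients affected cannot be estimated, because the documents give no rate of adrenal insufficiency or steroid use. The count of 19 is a per-subject ceiling that assumes every planned dose is given. It measures how often staff would have to resolve the conflict, not harm. No effect on the MPR analysis, the error rates or the sample size is shown. The correction should be made because it concerns a risk the protocol itself singles out and because it is simple.

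**What to change.** Add one sentence to section 5.5.2: corticosteroids given under 5.2.2.1, as prophylaxis or stress-dose cover, or under 5.2.2.7, to treat a CRS-like reaction, are permitted and are not grounds for removal from the trial. Once these uses are no longer prohibited, the condition in 5.7 on prohibited concomitant treatment would not apply to them.

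Leave the evaluability definition in 5.8 as it is. Doses and indications remain for the clinical team to decide. The cost is that one sentence, with no change to sample size, visits, data collection or analysis.

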## **5.6 Rescue Medications and Supportive Care**

### **5.6.1 Supportive Care Guidelines**

Subjects should receive appropriate supportive care measures as deemed necessary by the treating investigator. Suggested supportive care measures for the management of adverse events with potential immunologic etiology are outlined below. Where appropriate, these guidelines include the use of oral or intravenous treatment with corticosteroids as well as additional anti-inflammatory agents if symptoms do not improve with administration of corticosteroids. Note that several courses of steroid tapering may be necessary as symptoms may worsen when the steroid dose is decreased.

For each disorder, attempts should be made to rule out other causes such as metastatic disease or bacterial or viral infection, which might require additional supportive care. The treatment guidelines are intended to be applied when the investigator determines the events to be related to nivolumab.

Note: if after the evaluation the event is determined not to be related, the investigator does not need to follow the treatment guidance (as outlined below). **Refer to Section 5.2.1 for dose modification.**

It may be necessary to perform conditional procedures such as bronchoscopy, endoscopy, or skin photography as part of evaluation of the event.

- **Pneumonitis**
  - For **Grade 2 events**, treat with systemic corticosteroids. When symptoms improve to Grade 1 or less, steroid taper should be started and continued over no less than 4 weeks.
  - For **Grade 3-4 events**, immediately treat with intravenous steroids. Administer additional anti-inflammatory measures, as needed.
  - Add prophylactic antibiotics for opportunistic infections in the case of prolonged steroid administration.
- **Diarrhea/Colitis**
  - Subjects should be carefully monitored for signs and symptoms of enterocolitis (such as diarrhea, abdominal pain, blood or mucus in stool, with or without fever) and of bowel perforation (such as peritoneal signs and ileus).
  - All subjects who experience diarrhea/colitis should be advised to drink liberal quantities of clear fluids. If sufficient oral fluid intake is not feasible, fluid and electrolytes should be substituted via IV infusion. For Grade 2 or higher diarrhea, consider GI consultation and endoscopy to confirm or rule out colitis.
  - For **Grade 2 diarrhea/colitis**, administer oral corticosteroids.
  - For **Grade 3 or 4 diarrhea/colitis**, treat with intravenous steroids followed by high dose oral steroids.
  - When symptoms improve to Grade 1 or less, steroid taper should be started and continued over no less than 4 weeks.
- **Type 1 diabetes mellitus (if new onset, including diabetic ketoacidosis [DKA]) or ≥ Grade 3 Hyperglycemia, if associated with ketosis (ketonuria) or metabolic acidosis (DKA)**
  - For **T1DM** or **Grade 3-4 Hyperglycemia**
    - Insulin replacement therapy is recommended for Type I diabetes mellitus and for Grade 3-4 hyperglycemia associated with metabolic acidosis or ketonuria.
    - Evaluate patients with serum glucose and a metabolic panel, urine ketones, glycosylated hemoglobin, and C-peptide.
- **Hypophysitis**
  - For **Grade 2 events**, treat with corticosteroids. When symptoms improve to Grade 1 or less, steroid taper should be started and continued over no less than 4 weeks. Replacement of appropriate hormones may be required as the steroid dose is tapered.
  - For **Grade 3-4 events**, treat with an initial dose of IV corticosteroids followed by oral corticosteroids. When symptoms improve to Grade 1 or less, steroid taper should be started and continued over no less than 4 weeks. Replacement of appropriate hormones may be required as the steroid dose is tapered.

- **Hyperthyroidism or Hypothyroidism**
  - Thyroid disorders can occur at any time during treatment. Monitor patients for changes in thyroid function (at the start of treatment, periodically during treatment, and as indicated based on clinical evaluation) and for clinical signs and symptoms of thyroid disorders.
  - **Grade 2** hyperthyroidism events (and **Grade 2-4** hypothyroidism):
    - In hyperthyroidism, non-selective beta-blockers (e.g. propranolol) are suggested as initial therapy.
    - In hypothyroidism, thyroid hormone replacement therapy, with levothyroxine or liothyroinine, is indicated per standard of care.
  - **Grade 3-4** hyperthyroidism
    - Treat with an initial dose of IV corticosteroid followed by oral corticosteroids. When symptoms improve to Grade 1 or less, steroid taper should be started and continued over no less than 4 weeks. Replacement of appropriate hormones may be required as the steroid dose is tapered.
- **Hepatic**
  - For **Grade 2** events, monitor liver function tests more frequently until returned to baseline values (consider weekly).
    - Treat with IV or oral corticosteroids
  - For **Grade 3-4** events, treat with intravenous corticosteroids for 24 to 48 hours.
  - When symptoms improve to Grade 1 or less, a steroid taper should be started and continued over no less than 4 weeks.
- **Nephritis**
  - For **Grade 2** events, treat with corticosteroids.
  - For **Grade 3-4** events, treat with systemic corticosteroids.
  - When symptoms improve to Grade 1 or less, steroid taper should be started and continued over no less than 4 weeks.
- Management of infusion reactions
- Signs and symptoms usually develop during or shortly after drug infusion and generally resolve completely within 24 hours of completion of infusion.

**Table 5.6.1-1** below shows treatment guidelines for subjects who experience an infusion reaction associated with administration of nivolumab.

